643 longitudinal follow-up, the clinical center will be made aware of a subject's death. However,
644 some subjects will be lost to follow-up with their vital status unknown. For these subjects, staff
645 at the local clinical center or Administrative personnel at National Jewish Health (if subject
646 identifiers have been transferred) will conduct a search to determine vital status using subject's
647 stored social security numbers. This search may include a National Death Index query, Social
648 Security Death Index query and general internet search including obituary postings. Once vital
649 status has been confirmed as dead, the clinical center will obtain additional information
650 regarding the subject's death so that cause of death may be determined. This additional
651 information will include: 1) Informant Interview conducted with next of kin or other close
652 contact of the study participant or the subject's physician, 2) Death certificate, 3) Hospital
653 Discharge Summary if it is determined that the death occurred in hospital or within 3 months of a
654 hospitalization, and 4) Request for recent treating physician records if death did not occur in the
655 hospital.

656 The above records will be de-identified and transferred to the Data Coordinating Center. A
657 Mortality Adjudication Committee will review these records centrally. The data will be reviewed
658 by the Mortality Adjudication Committee and a final cause of death will be assigned.

659 **VII. BIOSTATISTICAL ANALYSIS**

660 In Phase 1, genome-wide association analysis was performed using genome-wide SNP genotypes
661 obtained in the entire COPDGene study population. In Phase 2, exome chip genotyping, and whole
662 genome sequencing data were obtained. In Phase 3, we will perform both longitudinal
663 epidemiology analysis and analysis of genetic and Omics data.
664

665 For longitudinal epidemiological analysis, the primary outcomes for COPD development and
666 progression are changes in FEV₁, CT emphysema [Adjusted Lung Density (PERC15 adjusted for
667 lung volume)], functional small airway disease by PRM, and all-cause mortality. In addition to
668 the "change" variables for lung function and imaging, we will average over repeated measures
669 for each outcome to increase power. Secondary outcome measures include respiratory mortality
670 and respiratory exacerbation frequency, as well as changes in CT airway wall thickness, CT gas

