671 trapping, six minute walk distance (6MWD), and health-related quality of life. Longitudinal
672 analyses will be performed with quantitative imaging phenotypes from the Phase 1, 2, and 3
673 visits. Key predictor variables to be assessed for these outcomes include age, gender, current
674 smoking status (at each visit), pack-years, baseline lung function, baseline CT emphysema and
675 airway measures, respiratory symptoms (e.g., chronic bronchitis, dyspnea), respiratory
676 medications, and co-morbid illnesses (including lung cancer and coronary artery disease).
677 Exacerbation frequency will be assessed as a predictor of primary outcome measures.
678 Transformations of CT and spirometric progression measures from among the Box-Cox family
679 of transformations will be considered to stabilize variance estimates across the ranges of CT
680 measurement values. We will compare the demographic and clinical characteristics of subjects
681 who have follow-up data to those subjects missing due to death and those subjects missing due to

682 loss to follow-up. Longitudinal analysis will be performed including time-dependent covariates
 683 such as change in current smoking status. Time-dependent covariates in these analyses include
 684 change in current smoking status and change in pulmonary medications. Disease progression and
 685 mortality will be simultaneously assessed to limit potential bias introduced by differential
 686 survival. This analytical approach considers the joint distribution of the vector of repeated
 687 measures (i.e., longitudinal progression of PFT abnormalities and CT measures) simultaneously
 688 with time to event (i.e., mortality) using the method developed by Hogan and Laird(10).
 689 The power to detect differences in 10-year changes between subtypes of COPDGen subjects
 690 was assessed for FEV₁, PERC15, adjusted lung density, and % gas trapping. These calculations
 691 used the mean and standard deviation (SD) with estimated changes in FEV₁(11), PERC15(12),
 692 adjusted lung density, and % gas trapping based on the 5-year follow-up visits. We assumed a
 693 significance level of 0.05 and equal variance of the change in each subtype group. These
 694 conservative calculations are based on comparing differences in rates of change for COPD-
 695 related phenotypes among two hypothetical groups of subjects ranging in size from 250 to 2000,

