 696 which will be created from the 4500 subjects with follow-up spirometry, clinical measures, and
 697 chest CT scans in Phase 3 (**Table 2**). Using these assumptions, there is adequate power to detect
 698 differences between subtype groups with as few as 250 subjects. By 2-sided log rank test, we
 699 will have virtually 100% power to detect a 15% difference in all-cause or cause-specific
 700 mortality between the slow and fast FEV₁ decline groups in Table 2.
 701

Table 2: Power (%) for Longitudinal Epidemiology Analysis

Outcome	Difference Between Groups over 10 yrs	Sample Size of Each Subtype Group for Pairwise Comparisons			
		250	500	1000	2000
FEV ₁ , ml	100	97	100	100	100
	200	100	100	100	100
PERC15	4	75	96	100	100
	8	100	100	100	100
Adjusted Lung Density	2	46	75	96	100
	4	96	100	100	100
% Gas trapping	2	70	94	100	100
	3	96	100	100	100

702
 703 The primary phenotypes for genetic, transcriptomic, and proteomic analysis will be each COPD
 704 subtype vs. smoking controls; the quantitative emphysema and airway disease axes; and the
 705 change in FEV₁ and adjusted lung density between the 5-year and 10-year visits. In addition, a
 706 number of secondary analyses will be performed, including: a) presence/absence of COPD
 707 (comparing subjects with GOLD 2-4 COPD to smoking controls); b) cross-sectional measures of
 708 CT emphysema, CT gas trapping, CT airway wall area, FEV₁, 6MWD, oxygen saturation,
 709 emphysema distribution, and chronic bronchitis; and c) longitudinal measures of exacerbation
 710 frequency and change in CT gas trapping, CT airway wall area, and 6MWD. Cross-sectional and
 711 longitudinal COPD-related phenotypes will be assessed within each COPD subtype and within
 712 the entire study population. Longitudinal imaging and lung function phenotypes will be assessed
 713 as both change over time (between the 5 and 10-year visits and across all three visits) and
 714 average outcomes over all three visits.
 715

716 Phase 2 blood RNA-Seq will be used to generate gene, exon, and isoform-level estimates of
 717 relative expression abundance. RNA-Seq data will be processed by the CDNM bioinformatics
 718 pipeline that addresses sequencing errors and other technical artifacts. Alignment to the human

719 reference genome will be performed with STAR(13), followed by multiple quantification and
720 analysis options, including DESeq2(14), DEXSeq(15), and voom/limma(16). While isoform-

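### Adequate power with 250 per subtype group is claimed without qualification, but Table 2 shows 46% to 75% for the smaller CT differences and does not cover PRM small airway disease

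*Protocol*

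**What the plan says.** Section VII (Biostatistical Analysis) names the primary longitudinal outcomes as changes in FEV₁ and in adjusted lung density, together with "functional small airway disease by PRM, and all-cause mortality". Gas trapping on CT is listed as secondary. Unadjusted PERC15 appears there only as the measure from which adjusted lung density is derived.

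The power calculation compares two hypothetical subtype groups of 250 to 2000 subjects each. It assumes a "significance level of 0.05 and equal variance of the change in each subtype group". The text then states that power is adequate to detect "differences between subtype groups with as few as 250 subjects".

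Table 2 follows, under the column heading "Sample Size of Each Subtype Group for Pairwise Comparisons". Its row for the smaller density difference reads "Adjusted Lung Density 2 46 75 96 100", that is, a difference of 2 units over ten years with 250, 500, 1000 and 2000 per group. Power at 250 per group for all rows is:

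| Outcome | Smaller difference | Power | Larger difference | Power |
|---|---|---|---|---|
| FEV₁ | 100 ml | 97% | 200 ml | 100% |
| PERC15 | 4 | 75% | 8 | 100% |
| Adjusted lung density | 2 | 46% | 4 | 96% |
| Gas trapping | 2 | 70% | 3 | 96% |

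**The concern.** The sentence is meant to summarise the table, yet three of the eight rows fall below 80% at 250 per group, and one of these, for a primary outcome, is below 50%. The Protocol sets no threshold for this analysis. Elsewhere in section VII, however, it uses 80% as its benchmark, both for the rare-variant analysis in African American subjects and for the biomarker comparison in the Short-Term Follow-Up Study.

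Someone planning subtype comparisons from the sentence alone would take 250 per group as enough for any tabulated difference. For 2 units of adjusted lung density, such a comparison would more often miss the difference than find it.

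There is also a gap in coverage. Of the three primary change outcomes, PRM functional small airway disease has no power figure, so the general statement has no support for it. All-cause mortality has its own log-rank statement and is not at issue here.

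**Working it through.** **Inputs.** From section VII and Table 2: significance level 0.05, equal variances, equal group sizes, and the tabulated differences and powers. Sidedness is stated only for mortality ("By 2-sided log rank test, we"), so a two-sided test is assumed for the changes and then checked. No SD is printed, so one is back-solved per outcome.

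**Step 1: reproduce the table.** With n per group and difference d, power = Φ(d / (SD·√(2/n)) − 1.960). Inverting this at the 46% cell, where z(0.46) = −0.100 and √(2/250) = 0.08944:

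SD = 2 / ((1.960 − 0.100) × 0.08944) = 12.0 (12.025 unrounded).

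That one SD gives, for adjusted lung density:

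| Difference | 250 | 500 | 1000 | 2000 |
|---|---|---|---|---|
| 2, recomputed | 46.0 | 74.9 | 96.1 | 100.0 |
| 2, Table 2 | 46 | 75 | 96 | 100 |
| 4, recomputed | 96.1 | 100.0 | 100.0 | 100.0 |
| 4, Table 2 | 96 | 100 | 100 | 100 |

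A t-test version gives the same powers with SD 12.00. A one-sided test fitted to the 46% cell gives 70.5% and 92.6% where the table has 75 and 96, so it is rejected. The 46% is therefore a consistent two-sided figure and not a misprint. The other outcomes also reproduce two-sided, with SDs of about 291 ml (FEV₁), 17.0 (PERC15) and 9.0 (gas trapping).

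**Step 2: what 250 per group detects with 80% power.** Since z(0.975) + z(0.80) = 1.960 + 0.842 = 2.802, the detectable difference is d × 2.802 / (1.960 + z(power at 250)):

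- FEV₁: 100 × 2.802 / (1.960 + 1.881) = 73 ml
- Adjusted lung density: 2 × 2.802 / (1.960 − 0.100) = 3.0 units
- PERC15: 4 × 2.802 / (1.960 + 0.674) = 4.3 units
- Gas trapping: 2 × 2.802 / (1.960 + 0.524) = 2.3 points

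**Step 3: group size for 2 units of adjusted lung density.** n = 2 × (z(0.975) + z(power))² × SD² / d², with SD² = 12.025² = 144.6:

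- 80%: 2 × 7.849 × 144.6 / 4 = 568 per group (560 to 576 when the 46% is allowed to lie between 45.5% and 46.5%)
- 90%: 2 × 10.507 × 144.6 / 4 = 760 per group

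By the same formula, 80% power needs about 283 per group for 4 units of PERC15 and about 318 for 2 points of gas trapping.

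**The case against.** The strongest reply is that every outcome reaches at least 96% at 250 per group for its larger tabulated difference, that the Protocol does not say which difference is the target, and that the exact powers stand directly below the sentence. The groups are hypothetical, no subtype is fixed at 250, and the cohort is already enrolled, so no recruitment decision rests on the sentence. All of this is true. It limits the point to an overstatement, but the sentence does not confine itself to the larger differences.

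The Protocol also calls the calculations conservative and plans to average repeated measures to gain power. Neither rescues the claim: the averaging is described as an addition to the change variables, and no gain is quantified for the changes in Table 2.

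Three stronger readings are tempting and are not supported:

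- A reader might take 46% as the power for adjusted lung density at 250 per group in general. It applies to 2 units; for 4 units the power is 96%.
- A reader might infer that five-year SDs were used unscaled for ten-year changes, so that true power is lower still. The Protocol prints no SD and no scaling rule. Its input sentence attaches literature citations to FEV₁ and PERC15, so the mention of the five-year visits may concern only adjusted lung density and gas trapping. Lower power cannot be derived from this.
- A reader might apply about 570 per group as a minimum for all CT comparisons. Table 2 contradicts that: at 500 per group it already gives 96% for 4 units of PERC15 and 94% for 2 points of gas trapping.

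**Conclusion.** The point holds in limited form. At 250 per group the unqualified claim fails for the smaller tabulated difference of all three CT measures (46%, 70% and 75%) and holds for both FEV₁ differences and for every larger CT difference. The most serious case is adjusted lung density, because it is a primary outcome and 2 units has only 75% power even at 500 per group. The claim also has no support for PRM functional small airway disease.

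The powers are the Protocol's own. The detectable differences and group sizes rest on SDs back-solved from rounded powers, on a two-sided test at 0.05 with equal groups, and on 80% as the meaning of adequate. The choice of 80% is an assumption for this analysis, though 46% would meet no usual threshold. What needs correcting is a stated property of the design; the design and data collection are unaffected.

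**What to change.** In section VII, replace the general sentence with one limited to what 250 per group supports at 80% power: about 73 ml FEV₁, 3.0 units of adjusted lung density, 4.3 units of PERC15 and 2.3 points of gas trapping. The Protocol's authors should confirm these against the SDs they used.

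Add that 2 units of adjusted lung density needs about 570 per group for 80% power and about 760 for 90%. State this for that outcome and difference only.

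State that the claim does not cover PRM functional small airway disease, or add a row for it to Table 2. The existing gas-trapping and PERC15 rows can stay.

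The cost is a few sentences, plus one calculation if the row is added. The only downside is that the stated power becomes less favourable.

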721 level resolution is most reflective of underlying biology, it is technically challenging to
722 accurately infer isoform levels from short-read fragments(17), and for some applications gene or
723 exon-level quantifications may be preferable to isoform quantification(14, 15). Gene-level
724 quantification of differential expression analysis will be performed using voom/limma, which
725 accounts for the distributional aspects of RNA-Seq data through a weighted regression approach.
726 Identification of differential exon usage will be performed using a novel implementation of
727 DEXSeq adapted for large studies. These tools are all implemented in R/Bioconductor. Isoform
728 quantification and differential expression analysis will be performed using pseudoalignment-
729 based methods such as kallisto(18) and sleuth for isoform quantification and differential
730 expression, respectively. Associations of gene expression to COPD subtypes will be adjusted for
731 covariates, including complete blood count differentials. Surrogate variable analysis will be used
732 to correct for potential batch effects and to remove unwanted sources of variability.(19)

733
734 For proteomics analysis, the relationships between the categorical and quantitative outcomes and
735 the predictor variables (~1310 individual plasma protein biomarkers in the SOMAScan panel)
736 are assessed using standard regression models. Covariates in these analyses include age, gender,
737 pack-years of smoking, and current smoking. To control the false discovery rate, the Benjamini-
738 Hochberg method is used to adjust the p-values. These biomarker measurements will be
739 integrated with pQTL genetic variants to improve accuracy of risk prediction.

740
741 COPD-related phenotypes will be assessed with whole genome sequencing (WGS) data for
742 possible associations with both rare and common variants. In addition, for each protein and
743 transcript that shows significant differences among COPD subtypes or between cases and control
744 subjects, both *cis* (within 1 Mb) and *trans* (genome-wide) association analysis will be performed
745 using WGS data. Although we will re-evaluate analytical methods for rare variants when our
746 Omics and WGS data become available, our current primary analysis plan is to test single
747 common and rare variants using linear regression or the Firth test, and the Sequence Kernel

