	20	40	60	80
Odds ratio of 2.25	24.3	43.1	68.2	82.7
Odds ratio of 2.5	32.1	58.8	84.9	95.4

773
 774
 775 We will also perform epidemiological and Omics analysis in 800 subjects from the Short-Term
 776 Follow-Up Study Population. The relationships between the outcomes of interest (FEV₁ and
 777 adjusted lung density) of each of the three high risk groups compared to the reference group will
 778 be assessed using linear mixed models. Covariates in these analyses will include risk group, visit,
 779 age, gender, pack-years of smoking, current smoking status, and baseline FEV₁ % predicted. The
 780 relationship between changes in FEV₁ and changes in adjusted lung density will be assessed by
 781 including time-varying as well as subject mean values in the model as predictors. An
 782 unstructured covariance structure (or other appropriate structure) will be used in the model to
 783 account for repeated measures. We will adjust for multiple statistical testing by requiring
 784 $p < 0.01$ to demonstrate any significant association.

785
 786 The power estimates to detect differences in change in FEV₁ or adjusted lung density for the
 787 Short-Term Follow-Up Study are shown in **Table 4**. Two rapid progression groups will be tested
 788 for change in FEV₁ (High COPD Progression Score and Paraseptal Emphysema) and two rapid
 789 progression groups will be tested for change in adjusted lung density (High Risk Airway Disease
 790 Axis and Paraseptal Emphysema). Based on the five-year changes in those groups compared to
 791 non-high risk subjects, 200 subjects per group will provide excellent power to detect differences
 792 between the rapid progression and non-high risk groups over one year. Power to detect
 793 differences for RNA-Seq and proteomic biomarkers between 200 rapid progression and 200 non-
 794 rapid progression subjects was assessed. We will have 80% power to detect effect sizes > 0.6
 795 standard deviations, which will be adequate to detect useful biomarkers.

796

Outcome	Rapid Progression Group	Sample Size of Each Short-Term Follow-Up Group		
		100	200	300
FEV ₁ , ml/yr	High COPD Progression Score	100	100	100
	Paraseptal Emphysema	72	95	99
Adjusted Lung Density, per yr	High Risk Airway Disease Axis	100	100	100
	Paraseptal Emphysema	100	100	100

797
798
799
800
801
802
803
804
805
806

VIII. RISKS AND DISCOMFORTS

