911 Jewish Health and in Utah, which will review de-identified spirometry data from each study
912 participant. Quality assurance of CT scans will be analyzed by the Imaging Core in Denver.
913 Questionnaires and other data will be quality controlled by the Data Coordinating Center in
914 Denver.

915 As noted above we anticipate that some subjects may expire during the next phase of this study
916 due to a combination of pre-existing disease and the onset of new conditions. These events are
917 not anticipated to be related to the study visit; however, they provide important information
918 about the natural history of COPD and other smoking-related conditions. We will monitor and
919 collect information about deaths in the cohort but will not report them to IRBs as study-related
920 events unless they occur during a study visit or within twenty-four hours of the study visit and
921 are judged to be related to a study procedure.

922 The COPDGene Administrative Core will hire National Research Coordinators. They will visit
923 each Clinical Center periodically to review site facilities, monitor study procedures and record
924 keeping, assist with continuing education of local coordinators to continue our excellent track
925 record of high quality study data and completeness, and as needed and when locally approved,
926 assist in conducting study visits. Clinical centers will be responsible for providing study records
927 and logs for review to the National Research Coordinators.

928 **XI. DATA STORAGE AND DISTRIBUTION**

929 The COPDGene study has nine study cores and twenty participating clinical centers. Clinical
930 centers send data to the Data Coordinating Center (DCC) at National Jewish Health, the
931 Biorepository at Brigham and Women’s Hospital, the Pulmonary Function Testing Center (PFT)
932 at NJH and to the Imaging Center at NJH.

933 The Administrative Center oversees and coordinates all study activities. The DCC maintains
934 confidentiality of all protected health information collected from study participants and stores
935 subject data. The Administrative Center releases data and Biospecimens to internal and external
936 study investigators. Internal Investigators consist of co-investigators at the twenty clinical
937 centers and at the study centers. The Ancillary Studies and Publications Committee oversee
938 distribution of data and Biospecimens to external investigators, outside of the COPDGene study.

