Any history of physician-diagnosed respiratory disease

One hundred and eight subjects with no smoking history and no airflow limitation were included as a reference population for comparison with those affected by smoking exposure. These subjects will offer information on the processes involved in normal lung aging. Non-smoking control subjects are critical for supporting genetic and pathological findings within smoking and diseased subject groups by acting as a baseline for normal pulmonary physiology within a genetically mixed population.

Subject Phase 1 Actual Enrollment:

Phase 1, which was performed from November 2007 until July 2012, enrolled 10,371 subjects. Of these subjects 3438 were African American and 6933 were Non-Hispanic White. Enrolled subjects classified by severity of lung disease were as follows:

Smoker Controls – 4391

GOLD 2 - 4 Subjects – 3692

GOLD Unclassified – 1258

GOLD 1 Subjects – 795

Non-smokers controls – 108

Lack final GOLD classification due to failed spirometry – 63

Significant ILD or bronchiectasis noted on CT scan, excluded from analysis – 64

All of the enrolled subjects had at least a 10 pack-year smoking history (except the non-smoker group) and were between 45 and 80 years of age. Enrollment of up to a total of 1500 non-smoker controls is still anticipated.

II. SUBJECT ENROLLMENT

Phase 1

This project will recruit a total of 12,000 subjects over five years from twenty-one clinical study centers. We anticipate recruitment will be completed early in the fifth year of the proposed study, allowing time for the genetic and epidemiologic analyses to occur by the end of the fifth year. Each Clinical Center will be expected to, on average, recruit approximately 160 subjects in each of the first four years meeting the program's defined recruitment goals for recruitment among both racial/ethnic classes, an approximately equal division of men and women, and with COPD subjects equally distributed among GOLD grades 1, 2, 3 and 4. The Executive Committee with the help of the Steering Committee will set and monitor goals for subject recruitment from each Clinical Center. The Administrative Core will have the right to modify recruitment goals among the centers to meet the overall goals of the project with respect to numbers of subjects recruited, minority subjects, or the balance of subjects in GOLD stages. The Administrative Core may incorporate additional qualified Clinical Centers if needed to meet recruitment goals.

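### The covariates named for the proteomic regressions omit race/ancestry and clinical centre, so protein-subtype associations can be confounded wherever both sides vary with either

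*Protocol*

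**What the plan says.** Protocol Section VII (Biostatistical Analysis) sets out the proteomic analysis in one paragraph. Outcomes are related by standard regression to "the predictor variables (~1310 individual plasma protein biomarkers in the SOMAScan panel"). On adjustment it says "Covariates in these analyses include age, gender", and the list ends with "pack-years of smoking, and current smoking. To control the false discovery rate, the Benjamini"-Hochberg method is applied to the p-values. Race, ancestry, clinical centre and assay batch are not mentioned, and the protein models are not described as stratified by race.

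The contrasts are set slightly earlier in the section: "The primary phenotypes for genetic, transcriptomic, and proteomic analysis will be each COPD" subtype against smoking controls, together with the quantitative emphysema and airway axes and the 5-to-10-year changes in FEV1 and adjusted lung density. Phenotypes are to be assessed within each subtype and in the whole study population.

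Both missing variables are known for every subject. Appendix A reports that "3438 were African American and 6933 were Non-Hispanic White". Section XI states: "The COPDGene study has nine study cores and twenty participating clinical centers. Clinical" centres then send their data and samples to the central cores.

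The neighbouring paragraphs do address unwanted variation. The RNA-Seq paragraph adjusts for blood-count differentials and uses surrogate variable analysis for batch effects. The sequencing paragraph adjusts for population substructure with a Jaccard-index method.

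**The concern.** Race and centre are the two plainest design variables of a two-race, multi-centre cohort, and the protocol's own text makes each a plausible confounder.

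- **Race.** Section III (New Non-Smoker Controls) argues that CT scans cannot be judged properly without knowing the effects of age, gender and race on healthy lungs. COPD subtypes rest partly on CT (Section I). The proteomic list takes up two of those three variables and leaves out race.
- **Centre.** Appendix A says sources of subjects will differ between centres, from inpatients to support groups. It also lets the Administrative Core shift recruitment goals among centres to balance minority numbers and GOLD stages. Centre can therefore be tied to disease status and to race. Blood is drawn locally, so centre is also the natural stand-in for any difference in sample handling, although the protocol describes no such difference.

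If subtype and control groups differ in racial or centre mix, a protein that varies with that mix can be declared a subtype biomarker with no relation to the subtype. False discovery rate control limits chance findings among the proteins tested. It does not protect against a systematic shift, and a larger sample makes such a shift easier to declare significant.

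**Working it through.** The protocol gives no figure that depends on the covariate list, so there is none to reproduce. The check has two parts.

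**1. Does any other text supply the missing adjustment?**

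- *Race/ancestry.* The substructure sentence in Section VII is worded to cover all analyses. It stands between the SKAT description and the trans-QTL tests, and it invokes a rare-variant method. It does not clearly reach a regression of subtype on protein level.
- *Race strata.* Separate power statements for non-Hispanic White and African American subjects appear only for the rare-variant genetic analysis.
- *Centre.* No model anywhere in the protocol includes it.
- *Batch or unwanted variation.* Surrogate variable analysis is stated for gene expression only.

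**2. How large could the effect be?** This is an illustration for race. No figure is available for centre.

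Inputs from the protocol:
- African American share: 3438 / 10,371 = 0.3315, about one third (Appendix A).
- Proteins: about 1310 (Section VII).
- Group sizes, case A: 200 against 200, the only proteomic sample size stated. It belongs to the rapid-progression comparison (Section VII).
- Group sizes, case B: 0.25 x 3692 = 923 against 4391. The 25% is borrowed from the genetic power simulation; 3692 (GOLD 2-4) and 4391 (smoker controls) are in Appendix A. The number of subjects to be assayed for the subtype comparison is not stated.

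Assumed inputs, not in the documents:
- difference in African American share between groups after the named covariates: 0 to 20 points;
- difference in protein level between races: 0 to 0.5 SD.

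Formulas, with protein level in SD units:
- bias = share difference x protein difference by race
- SE = sqrt(1/n1 + 1/n2); case A: sqrt(2/200) = 0.100; case B: sqrt(1/923 + 1/4391) = 0.0362
- false-positive rate at two-sided 0.05 = P(|Z + bias/SE| > 1.96)

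| Share difference | Protein difference | Bias (SD) | Case A | Case B |
|---|---|---|---|---|
| 0 | any | 0 | 5.0% | 5.0% |
| 10 points | 0.3 SD | 0.03 | 6.0% | 13.2% |
| 10 points | 0.5 SD | 0.05 | 7.9% | 28.2% |
| 20 points | 0.3 SD | 0.06 | 9.2% | 38.1% |
| 20 points | 0.5 SD | 0.10 | 17.0% | 78.9% |

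At the strictest threshold relevant to 1310 tests, 0.05/1310 = 3.8e-5, the last row gives 0.09% in case A and 8.7% in case B, against 0.0038% with no bias.

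**The case against.** The strongest reply is that the covariate sentence says its covariates include the four named, so the list is open, and that a complete list for an omics regression may sit in a statistical analysis plan that is not shown. This is right as far as it goes: a reader might infer that the models adjust for these four variables and nothing else, and the text does not say that. The protocol nevertheless chose to print a list, and two obvious design variables are not on it. An analyst following the text as written would leave them out.

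Second, the substructure sentence can be read as reaching every analysis. It does cover the later step that relates declared proteins to genetic variants, because that step is described in the same paragraph. A reader might infer that the protein-variant analyses are also unprotected against ancestry; they are not. Whether the sentence reaches the protein-subtype regressions is unclear, and it does not cover centre.

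Third, the illustration depends on assumptions. The documents give no racial mix by subtype and no protein difference by race, and 923 is a borrowed figure. In case B, 20 points x 0.5 SD gives z = 0.10/0.0362 = 2.76, p about 0.006. At an assumed 5% false discovery rate, that passes Benjamini-Hochberg only if about 150 of the 1310 proteins are declared (0.006 x 1310 / 0.05 is about 157; with the unrounded p it is about 150). A more extreme 30 points x 0.5 SD gives z = 4.14 in case B but only 0.15/0.100 = 1.5 with 200 against 200. All of this stands, and it is why the size must be called unknown.

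Two further extensions are tempting and not supported. A reader might infer that body mass index belongs in the list as well. The protocol links body composition to COPD features (Section V, hand grip strength), so it may lie on the disease pathway, and adjusting for it could remove real signal. A reader might also carry the point over to the Short-Term Follow-Up model, which lists "age, gender, pack-years of smoking, current smoking status, and baseline" FEV1 % predicted and likewise names neither race nor height. That analysis targets change in a repeated-measures model. Main effects of variables fixed within a subject shift the level and barely move the change.

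**Conclusion.** The point holds in a limited form. The named proteomic covariates leave out race/ancestry and clinical centre, both recorded, and no other text clearly supplies the first or supplies the second at all. Associations are at risk only where protein and outcome both vary with race or centre given age, gender, pack-years and current smoking. A reader might infer that every protein-subtype association is biased; the documents do not show that.

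The size cannot be taken from the documents. Over the assumed ranges the bias from race is 0 to 0.10 SD. The per-protein false-positive rate at nominal 0.05 then runs from 5% to 17% with 200 per group, and from 5% to 79% with the borrowed 923 against 4391. No range is offered for centre. The case for acting is that this confounding is avoidable at almost no cost, not that harm of a particular size has been shown.

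**What to change.** In the proteomics paragraph of Section VII, add race (or genetic ancestry components) and clinical centre to the named covariates. Also say whether the substructure adjustment in the sequencing paragraph is meant to reach the protein-subtype regressions, so that the two paragraphs agree. For each protein declared significant, report the estimate separately in African American and non-Hispanic White subjects.

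The cost is about 20 degrees of freedom (19 for twenty centres plus 1 for race, slightly more with several ancestry components), small against the cohort size, and a modest amount of extra reporting. No new data are needed. Body mass index need be no more than a sensitivity analysis, and the Short-Term Follow-Up model can stay as it is on this point.
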